5.3.2 Exclusion Criteria

Subjects are not eligible for this trial if they fulfill any of the following exclusion criteria:

1. Any condition that in the Investigator's opinion constitutes an inappropriate risk or a contraindication for participation in the trial or that could interfere with the trial objectives, conduct, or evaluation.
2. Renal impairment (glomerular filtration rate [GFR] < 45 mL/min/1.73 m² as calculated by the Modification of Diet in Renal Disease equation) calculated by the central laboratory as follows:

$$\text{GFR (mL/min per 1.73 m}^2\text{)} = 175 \times \text{standardized serum creatinine}^{-1.154} \times \text{age}^{-0.203} \times 1.212$$

(if black) \times 0.742 (if female)

3. Urine dipstick with $\geq 3+$ protein and urine protein:creatinine ratio > 2 mg/mg. Urine protein:creatinine ratio will be determined only if urine dipstick indicates $\geq 3+$ protein.
4. Known diagnosis of obstructive lung disease/emphysema as defined by forced expiratory volume in 1 second (FEV₁)/FVC ratio < 0.65 and/or significant emphysematous change on screening HRCT according to the central reader.
5. Other clinically significant abnormalities on HRCT not attributable to scleroderma or emphysema as defined above, which in the Investigator's opinion make enrollment in the trial inappropriate.
6. Known diagnosis of other significant respiratory disorders in the opinion of the Investigator.
7. Pulmonary hypertension that fulfills at least one of the following:
 - Currently being treated with systemic therapy targeted to PAH or pulmonary hypertension;
 - Considered by the Investigator to require initiation of systemic targeted PAH therapy;
 - History of transthoracic echocardiography showing at least one of the following (unless right heart catheterization subsequent to these measures did not reveal pulmonary hypertension): tricuspid regurgitation jet > 2.8 m/sec, right atrial enlargement (major dimension > 53 mm), right ventricular enlargement (mid cavity dimension > 35 mm), moderate to severe left ventricular dysfunction;
 - At screening, N-terminal prohormone brain natriuretic peptide (NT pro-BNP) $> 3 \times$ the upper limit of normal (ULN), unless, for example, right heart catheterization performed within 3 months of the Screening Visit did not reveal pulmonary hypertension.
8. Current clinical diagnosis of another inflammatory connective tissue disease (eg, systemic lupus erythematosus, rheumatoid arthritis, ankylosing spondylitis, or dermato/polymyositis); concomitant scleroderma-associated myopathy, fibromyalgia, and secondary Sjögren's syndrome are allowed.
9. Clinical suspicion of or recent evidence of significant aspiration within the previous 6 months, such as chemical induced pneumonitis or aspiration pneumonia.
10. Active clinically significant viral, bacterial, or fungal infection, or any major episode of infection requiring hospitalization or treatment with parenteral anti-infectives within 4 weeks prior to screening or during the Screening Period, or completion of oral anti-infectives within 2 weeks before screening or use of oral anti-infectives during the Screening Period. Vaginal candidiasis, onychomycosis, and chronically suppressed oral

herpes simplex virus would not be exclusionary. Prophylaxis for *Pneumocystis jiroveci* pneumonia according to local guidelines will be permitted.

11. History of or positive human immunodeficiency virus (HIV), hepatitis C antibody and/or polymerase chain reaction or hepatitis B surface antigen (HBsAg) and/or hepatitis B core antibody (total and/or immunoglobulin M [IgM]) antibody at screening.
12. History of or current diagnosis of active tuberculosis (TB), or untreated latent TB infection (LTBI), determined by a TB skin test with purified protein derivative as evidenced by induration ≥ 5 mm or a positive QuantiFERON-TB or positive or borderline T-SPOT (Elispot) test performed locally, or centrally as needed, either at screening or documented with results within 3 months of the Screening Visit. Subjects who have previously completed appropriate and documented LTBI treatment or who are undergoing current treatment for LTBI will not be required to be tested.

If the subject is undergoing current treatment for LTBI, they must have received at least 4 continuous weeks of an appropriate LTBI treatment prior to the Screening Visit (ie, start of trial treatment) without evidence of re-exposure. If on LTBI treatment at the Screening Visit, the subject will be expected to complete an appropriate LTBI treatment regimen to remain in the trial:

- Subjects with current household contacts with active TB will also be excluded unless treated and evidence of household contacts being treated;
 - Indeterminate QuantiFERON-TB or T-SPOT tests may be repeated once, and will be considered positive if retest results are positive or indeterminate.
13. Presence of uncontrolled or New York Heart Association (NYHA) Class 3 or 4 congestive heart failure (refer to [Appendix III](#)).
 14. History of cancer, except adequately treated (ie, no evidence of recurrence within 5 years prior to screening) basal cell or squamous cell carcinomas of the skin (no more than 3 total in lifetime) or carcinoma in situ of the cervix.
 15. Known hypersensitivity to abituzumab or any component of the formulated abituzumab.
 16. Current smoker (including e-cigarettes) or smoking within 4 weeks of screening.
 17. Use of agents other than mycophenolate (MPS or MMF) considered by the Investigator to have immunomodulating, immunosuppressive, or potential scleroderma disease-modifying properties within 2 months of the Screening Visit. Examples of these agents include, but are not limited to, pirfenidone, nintedanib, methotrexate, azathioprine, leflunomide, calcineurin inhibitors, D-penicillamine, Potaba, and AIMSPRO. The use of cyclophosphamide within 5 months of the Screening Visit is not permitted. Hydroxychloroquine or chloroquine are permitted if dose has been stable for at least 4 weeks before the Screening Visit.

18. Use of systemic corticosteroids above 10 mg/day prednisone equivalent within 4 weeks of screening, during the Screening Period, or expected during the treatment period. Inhaled corticosteroids are not considered systemic and are permitted. Topical corticosteroids are permitted.
19. Use of any biologic agent within 12 weeks or 5 half-lives, whichever is longer, of screening.
20. History of anti-CD20 B-cell depleting therapy, eg, rituximab or ocrelizumab, within 6 months prior to the Screening Visit.
21. Use of any anticoagulant or antiplatelet agent (aspirin \leq 350 mg daily is permitted).
22. Clinically significant or predefined abnormalities in laboratory tests:
 - Aspartate aminotransferase (AST), alanine aminotransferase (ALT), or alkaline phosphatase (AP) level $> 2.5 \times$ ULN;
 - Total bilirubin $> 1.5 \times$ ULN (other than that due to known Gilbert's disease);
 - Hemoglobin < 5.0 mmol/L (9 g/dL), white blood cell count $< 2.5 \times 10^9/L$, or platelets $< 100 \times 10^9/L$;
 - International normalized ratio (INR) or partial thromboplastin time (PTT) $> 2.0 \times$ ULN;
 - Thyroid-stimulating hormone (TSH) < 0.01 or ≥ 7.1 mIU/L.
23. Individuals who cannot receive intravenous infusions (ie, difficult venous access).
24. History of alcohol or drug abuse for 1 year prior to screening in the opinion of the Investigator.
25. Pregnancy (documented by serum pregnancy test at screening or urine pregnancy test on Day 1) and/or breastfeeding/lactation within 3 months of the Screening Visit.
26. Subjects with a past medical history of thrombotic, thromboembolic, or abnormal bleeding events including concomitant antiphospholipid antibody syndrome (per Sydney classification criteria ([Gomez-Puerta 2014](#), [Miyakis 2006](#))). Subjects should be questioned specifically for thrombosis, phlebitis, embolism, etc. at screening to establish negative history. Subjects with known lupus anticoagulant and/or anticardiolipin and/or anti-b2 glycoprotein antibodies alone should not be excluded.
27. Legal incapacity or limited legal capacity.
28. Receipt of a live/attenuated vaccine within 12 weeks prior to the Screening Visit or subjects who are expecting to receive any live virus or bacterial vaccinations during the trial, or up to 3 months after the last dose of study drug, are not permitted. Seasonal influenza vaccination is permitted if the inactivated vaccine formulation is administered.

29. Major surgery requiring hospitalization within 4 weeks prior to the Screening Visit and any planned major surgery for the duration of the trial. Subjects with a history of lung resection.
30. Have a history of a major organ transplant (eg, heart, lung, kidney, or liver) or hematopoietic stem cell/marrow transplant or are due to receive transplantation.
31. Severe gastrointestinal disease requiring parenteral nutrition.

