5.4 Criteria for Initiation of Trial Treatment

All subjects who meet the inclusion and none of the exclusion criteria are eligible for randomization to one of the treatment groups.

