5.5 Criteria for Subject Withdrawal

5.5.1 Withdrawal from Trial Therapy

A subject must be withdrawn from IMP if any of the following occur:

- Enrollment despite violation of an inclusion and/or exclusion criterion which, in the Investigator's and/or Sponsor's opinion, makes discontinuation of the subject necessary.
- Participation in any other interventional trial during the duration of this trial for which the Investigator or Sponsor considers discontinuation of the IMP necessary.
- Occurrence of pregnancy.
- Anaphylaxis, anaphylactoid, or other severe or life-threatening hypersensitivity reactions to IMP, based on Investigator judgment. Such cases should be discussed with the Medical Monitor.
- Occurrence of any other AE for which discontinuation of IMP is desired or considered necessary by the Investigator, Sponsor, and/or the subject.
- Noncompliance, judged as significant by the Investigator or Sponsor including noncompliance with the required trial considerations.
- Discontinuation of LTBI therapy before complete, if present at the Screening Visit.
- Surgery considered by the Investigator or Sponsor to be major.
- Occurrence of any other clinical condition or circumstances for which discontinuation is considered necessary by the Investigator and/or the Sponsor/designee.
- Significant disease progression which in the Investigator's opinion requires initiation of rescue therapy, such as cyclophosphamide or other local standard of care treatment (see Section 6.5.5) or other new treatment considered to have immunosuppressive or immunomodulating properties.

If a subject discontinues IMP, then the subject should complete the early termination visit and then the remaining scheduled visits. At a minimum, the subject is expected to complete the trial

visits at Weeks 12, 24, 36, 52, 64, 76, 88, and 104, as well as the Safety Follow-up period Week 12 visit. Subjects with discontinued IMP can come to the other scheduled visits during the trial period according to the Investigator's judgment.

Subjects who withdraw from the treatment period would have an early termination visit followed by entrance into the Safety Follow-up Period.

Subjects who withdraw from the trial (eg, withdraw consent, lost to follow-up, or death; see Section 5.5.2) would not have any additional trial visits.

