7.4.3 Clinical Laboratory Assessments

The Sponsor should receive a list of laboratory normal ranges before shipment of IMP. Any change in laboratory normal ranges during the trial should be forwarded to the Sponsor and PPD .

Blood and urine samples will be collected for the clinical laboratory tests in [Table 4](#), following the timing noted in the Schedule of Assessments ([Table 1](#) and [Table 2](#)). All samples should be clearly identified. Samples will be collected, processed, and stored in accordance with the directions provided in the [PPD](#) Flow Chart. Urine pregnancy tests analyses are to be performed locally. All other parameters will be analyzed at the central laboratories.

Table 4 Clinical Laboratory Testing

Clinical Chemistry	Routine Hematology	Urinalysis (dipstick)
Gamma glutamyl transferase	Hematocrit	pH
ALT	Hemoglobin	Specific gravity
Albumin	Mean cellular hemoglobin	Leukocytes
AP	Mean cellular hemoglobin concentration	Nitrite
AST		Glucose
Bilirubin – direct (only if total bilirubin is outside the normal range)	Mean cellular volume	Ketones
	Platelet count	Protein
Bilirubin – total	Red blood cell count	Blood
Calcium	Red cell distribution width	
Chloride	White blood cell count and differential	Additional Urinalysis
Bicarbonate		Urine protein:creatinine ratio (performed if dipstick urinalysis reveals at least 3+ protein)
Serum creatinine		
Glucose	Coagulation (at screening only)	Microscopy if blood present
Potassium	Prothrombin time	
Protein – total	Activated partial thromboplastin time	Immunogenicity
Sodium		Anti-abituzumab antibodies
Urea		
Uric acid		
C-reactive protein		
TSH (at screening only)		
NT pro-BNP (at screening only)		

ALT = alanine aminotransferase, AP = alkaline phosphatase, AST = aspartate aminotransferase, NT pro-BNP = N-terminal prohormone brain natriuretic peptide, TSH = thyroid-stimulating hormone.

Other laboratory assessments include the following:

- Serum pregnancy test in female subjects of childbearing potential;
- Urine pregnancy test in female subjects of childbearing potential, to be performed locally;
- HIV, hepatitis C, and hepatitis B (HBsAg, hepatitis B core antibody [IgM and total]) serologies;
- HbA_{1c} may be evaluated for subjects with diabetes, at the discretion of the Investigator, and by forwarding a prior request to the Medical Monitor and notification to the Sponsor's

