8.4.2 Intent-to-Treat

The Intent-To-Treat (ITT) Population will consist of all randomized subjects. Subjects will be analyzed according to their randomized treatment.

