18.2 Listings

16.2.1: Subject Disposition

Listing 16.2.1.1: Subject Disposition and Withdrawals - Screening Analysis Set

Treatment Group	Subject Identifier	Screening Date	Randomized?/ Date Randomized/ Stratification Factor (a)	Withdrew Prior to Being Treated?	In SAF Analysis Set?	Withdrew from trial treatment/ Reason for Withdrawal	Date of Last Dose	Discont- inued Trial?/ Primary Reason	Date Discont- inued
Treatment A	XXXXXXX	DDMMYYYY	Yes/DDMMYYYY/ FVC <70%	XXX	XXX	Yes/XXXXXXXX XXXX	DDMMYYYY	Yes/ xxxxxxx	DDMMYYYY
	XXXXXXX	DDMMYYYY	Yes/DDMMYYYY/ FVC ≥70%	XXX	XXX	No		No	
	XXXXXXX	DDMMYYYY	Yes/DDMMYYYY/ XXXXXX	XXX	XXX	No		No	
								
Treatment B	XXXXXXX	DDMMYYYY	Yes/DDMMYYYY/ XXXXXX	XXX	XXX	No		No	
	...								
Etc.									

(a) Stratification Factor from eCRF: FVC <70% = Baseline FVC <70% predicted, FVC ≥70% = Baseline FVC ≥70% predicted.
Note: Baseline is defined as the last non-missing assessment value prior to randomization.

Programming Note: If a subject is screened but not yet randomized, treatment group will be Not Randomized. If they are screen failed then treatment group is Screen Failures.
If there are subjects in the Not Randomized group then add the following footnote (note indentation to line up with baseline footnote):

'Not Randomized' treatment group contains subjects who are still in screening at time of data cutoff.
Ensure any "Other" reasons for treatment and trial termination are specified, "Other: xxxxxx".

16.2.1: Subject Disposition
Listing 16.2.2.1: Important Protocol Deviations - ITT Analysis Set

Treatment Group	Subject Identifier	Type	Deviation details
Treatment A	XXXXXXX	Eligibility and Entry Criteria	XXXXXXXXXXXXXXXXX/ XXXXXXXXXXXXXXXXXXXXX
		Efficacy Criteria	XXXXXXXXXXXXXXXXXXXXX
	XXXXXXX	XXXXXXXXXXXXX	XXXXXXXXXXXXXXXXXXXXX
	XXXXXXX	XXXXXXXXXXXXX	XXXXXXXXXXXXXXXXXXXXX
		XXXXXXXXXXXXXXXXXXXXX
Treatment B	XXXXXXX	XXXXXXXXXXXXX XXXXXXXXXXXXX	XXXXXXXXXXXXXXXXXXXXX XXXXXXXXXXXXXXXXXXXXX
Etc.	...		

Programming note: Present each deviation on a new line.

16.2.4: Demographic Data
Listing 16.2.4.1: Subject Demographics - SAF Analysis Set

Treatment Group	Subject Identifier	Sex	Birth Date	Age (years)	Race	Ethnicity
Treatment A	XXXXXXX	Male	DDMMYYYY	XX	XXXXXXX	XXXXX
	XXXXXXX	Female	YYYY	XX	XXXXXXX	XXXXX
	XXXXXXX	XXXX	DDMMYYYY	XX	XXXXXXX	XXXXX
					
Treatment B	XXXXXXX	XXXX	DDMMYYYY	XX	XXXXXXX	XXXXX
	...					
Etc.						

Note: Age is relative to the date of informed consent.

16.2.4: Demographic Data

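### Exclusion criterion 22 states one hemoglobin limit in two units that do not agree: 5.0 mmol/L is about 8.1 g/dL, not 9 g/dL

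*Protocol*

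**What the plan says.** Criterion 22 in Protocol Section 5.3.2 covers "Clinically significant or predefined abnormalities in laboratory tests" and includes "Hemoglobin < 5.0 mmol/L (9 g/dL" as one of its numeric limits. The form, one value followed by another in parentheses, presents a single cut-off in two units.

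The limit is decisive for entry. Section 5.3.2 opens with "Subjects are not eligible for this trial if they fulfill any of the following exclusion criteria", and Section 5.4 states: "All subjects who meet the inclusion and none of the exclusion criteria are eligible for randomization to one of the treatment groups". One exclusion criterion met is therefore enough to bar a subject.

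No other part of the protocol or the SAP addendum restates the hemoglobin eligibility limit, gives a conversion factor, or says which unit takes precedence. The amendment entries reproduced in Appendix V change other exclusion criteria (8, 10, 16, 18 and 28 to 30 in Amendment 3; 7, 17, 20, 29 and 31 in Amendment 5) but not this line. Amendment 4 is not reproduced. The line is current text.

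**The concern.** A limit given in two units should be the same limit whichever unit is read. Here the mmol/L figure is the more permissive of the two. A site or laboratory working in mmol/L would admit subjects whom one working in g/dL would exclude.

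At stake is the eligibility of subjects in the band between the two figures, and how anemia is screened before treatment starts. There is also a record-keeping consequence. SAP addendum Section 8.1 plans a blinded meeting before database lock to confirm protocol deviations, and the addendum includes "Listing 16.2.2.1: Important Protocol Deviations - ITT Analysis Set". For a randomized subject in the band, the protocol as written does not determine whether an eligibility deviation occurred.

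**Working it through.** **Inputs**

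- Molar limit: 5.0 mmol/L (Protocol Section 5.3.2, criterion 22).
- Mass limit: 9 g/dL (same line).
- Conversion factor M in g/mmol: not in the documents, so an assumption. Base value 16.1145 g/mmol per heme unit, range 16.0 to 16.7.

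**Formulas**

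- g/dL = mmol/L × M / 10
- mmol/L = g/dL × 10 / M

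**Step 1: try to reproduce the stated equivalence**

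For 5.0 mmol/L to equal 9 g/dL exactly, M would have to be 90 / 5.0 = 18.0 g/mmol, which is outside the assumed range. The pair is not reproduced.

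**Step 2: convert each figure**

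| M (g/mmol) | 5.0 mmol/L in g/dL | 9 g/dL in mmol/L | Gap (g/dL) | Gap as % of 9 g/dL |
|---|---|---|---|---|
| 16.0 | 5.0 × 16.0 / 10 = 8.00 | 90 / 16.0 = 5.625 | 1.00 | 11.1% |
| 16.1145 | 5.0 × 16.1145 / 10 = 8.057 | 90 / 16.1145 = 5.585 | 0.943 | 10.5% |
| 16.7 | 5.0 × 16.7 / 10 = 8.35 | 90 / 16.7 = 5.389 | 0.65 | 7.2% |

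In molar units the gap at the base value is 5.585 − 5.0 = 0.585 mmol/L.

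**Step 3: could rounding explain it?**

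The largest value that rounds to 5.0 mmol/L is 5.05, and the smallest that rounds to 9 g/dL is 8.5. Rounding explains the pair only if 5.05 mmol/L reaches 8.5 g/dL.

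| M (g/mmol) | 5.05 mmol/L in g/dL | 8.5 g/dL in mmol/L |
|---|---|---|
| 16.0 | 8.08 | 5.31 |
| 16.1145 | 8.14 | 5.27 |
| 16.7 | 8.43 | 5.09 |

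Every value in the second column is below 8.5, and every value in the third is above 5.05. The break-even factor is 85 / 5.05 = 16.83 g/mmol, above the top of the range.

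**Step 4: could a different molar basis explain it?**

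On a tetramer basis (assumed M of about 64.458 g/mmol), 5.0 mmol/L is 5.0 × 64.458 / 10 = 32.2 g/dL. That does not match 9 g/dL either.

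**Step 5: the affected band**

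Subjects with hemoglobin of at least about 8.1 g/dL (lower end 8.0 to 8.35 over the range of M) and below 9.0 g/dL are excluded by the g/dL figure and not by the mmol/L figure.

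**The case against.** The mismatch itself is hard to contest; the stronger objections concern how much it matters.

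- **Central measurement.** Protocol Section 7.4.3 has urine pregnancy tests done locally and then says: "All other parameters will be analyzed at the central laboratories". One cut-off was therefore probably applied to everyone, and divergence between sites is unlikely. This stands, but it does not show which cut-off was used or that it was the intended one.
- **Clinical discretion.** Criterion 1, and the reference to clinical significance in criterion 22 itself, let an Investigator exclude a worrying hemoglobin whichever figure applies. This stands as protection for the subject. It does not make a predefined limit determinate.
- **No forced withdrawal.** Section 5.5.1 withdraws IMP for "Enrollment despite violation of an inclusion and/or exclusion criterion which, in the Investigator's and/or Sponsor's opinion, makes discontinuation of the subject necessary", so a wrongly enrolled subject could stay on treatment. This stands.
- **No effect on the analysis.** The trial ended early. The SAP addendum drops the per-protocol set and computes only summary statistics, with no tests or confidence intervals. This stands: no reported efficacy or safety summary depends on the limit.
- **A reading error.** The text was extracted from PDF, the limit appears only once, and 5.6 differs from 5.0 by one digit. This cannot be excluded, but nothing shows that it happened. A look at the source page would settle it.
- **The deviation check may already be covered.** The blinded review meeting exists to confirm deviations, and the listing covers only important ones, defined in a Study SAP that is not among these documents. So it cannot be said that a value in this band would be listed. The meeting still needs one limit to judge against.

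Neither figure can be presumed to govern. The mmol/L value is printed first, while the SAP shell for Table 15.3.5.3 reports hemoglobin in g/L, a mass unit. Neither observation settles the intent.

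**Conclusion.** The concern holds. The two hemoglobin limits in criterion 22 differ by 0.94 g/dL (0.59 mmol/L) at 16.1 g/mmol, and by 0.65 to 1.0 g/dL over 16.0 to 16.7 g/mmol. The conclusion rests on that assumed factor, since the documents supply none. It would fail only if the factor were at least 16.83 g/mmol.

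The error sits in a threshold that decides entry, so it should be corrected, but its consequence is limited. It touches eligibility and safety screening for subjects between about 8.1 and 9.0 g/dL. How many such subjects there were is unknown and may be zero. Sample size, power and the planned summaries are unaffected.

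**What to change.** State one consistent limit in criterion 22: either below 5.6 mmol/L (9 g/dL) or below 5.0 mmol/L (8.1 g/dL). The clinical team should choose; this review takes no view on which is right. Use the same value in the central laboratory's eligibility flag.

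Because the trial has stopped, the useful step now is to ask the central laboratory which value it applied. Then check randomized subjects with screening hemoglobin from about 8.1 to below 9.0 g/dL before the deviations are confirmed. The check belongs to the ITT set used for Listing 16.2.2.1, defined in Protocol Section 8.4.2 as follows: "The Intent-To-Treat (ITT) Population will consist of all randomized subjects".

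The cost is one corrected protocol line, one laboratory query and a short data check. No analysis changes.
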